1.2 SCHEMA

1.3 SCHEDULE OF ACTIVITIES (SOA)

Procedures	Screening* Day -7 to -3 (Participants washing out stimulants only)	Enrollment / Baseline* Day 0	Treatment Days 1 to 27	Follow Up Day 28 +3 days
Parent Informed consent		X		
Child Assent		X		
Mini-International Neuropsychiatric Interview for Children and Adolescents (MINI-KID)		X		
Demographics	X			
Medical history	X			
Wechsler Intelligence Scale for Children V (WISC V)		X		
Ishihara Colorblindness Test		X		
Vanderbilt ADHD Diagnostic Parent Rating Scale (Initial and Follow-Up)		X		X
Social Communication Questionnaire		X		
Short Sensory Profile		X		
Social Competence Scale		X		X
Video Game Play Questionnaire		X		
Behavior Assessment for Children, Second Edition (BASC-2)		X		
Beery Visual Motor Integration (VMI)		X		
Adaptive Cognitive Evaluation (ACE) [†]		X		X
Neuroracer [†] -locked EEG		X		X
Resting State EEG		X		X
AKL-M01 (AKL-T01 Monitor) [†]		X		X
Test of Variables of Attention (TOVA) [†]		X		X
Basic Response Time (BRT)		X		X
Administer AKL-T01		X		
AKL-T01 Compliance Monitoring			X	
Adverse Event (AE) Assessment				X
Complete Case Report Forms (CRFs)	X	X	X	X

* Screening and Baseline visits may be a combined visit for participants not washing out stimulant medication.

[†] Interventions are computerized

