3 OBJECTIVES AND ENDPOINTS

OBJECTIVES	ENDPOINTS
Primary	
Demonstrate enhancement of MFT power measured by stimulus-locked EEG (Perceptual Discrimination Task (PDT)=Stimulus) in children with ADHD following 4 weeks of at-home AKL-T01 treatment.	Change in midline frontal theta power as measured by PDT-locked EEG.
Secondary	
Demonstrate normalized MFT power in children with ADHD following 4 weeks of at-home AKL-T01 treatment.	MFT power of ADHD cohort at Day 28 compared to that of neurotypical cohort at Day 0 (historical controls).
Exploratory	
Demonstrate improvement in attention in children with ADHD following 4 weeks of at-home AKL-T01 treatment.	
Reaction time and reaction time variability as measured by TOVA.Reaction time and reaction time variability as measured by perceptual discrimination task.Reaction time and reaction time variability as measured by ALK-M01 Assessment.

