4 STUDY DESIGN

4.1 OVERALL DESIGN

This study is a single arm, open-label, pilot study to assess midline frontal theta (MFT) power as measured by stimulus-locked electroencephalogram (EEG) before and after treatment with AKL-T01 for improving attention in pediatric participants ages 8-12 years old with attention deficit hyperactivity disorder (ADHD).

All participants enrolled in this study will not be taking ADHD medications, including stimulants, for the duration of the study. Participants who are taking ADHD medications prior to Day 0 must have been stable off of medications for at least 30 days per parent report, or washout of medications at a Screening visit 3 – 7 days prior to Day 0.

At Baseline / Day 0, all eligible participants will complete both resting-state and PDT-locked EEG, as well as the TOVA, Vanderbilt, and AKL-M01 assessments.

All participants will then play AKL-T01 for approximately 25 minutes per day, 5 days per week, for 4 weeks at home.

At Follow-up / Day 28, participants will repeat both resting-state and PDT-locked EEG, as well as the TOVA, Vanderbilt, and AKL-M01 assessments.

All study visits for each participant should be completed during the same time of day (either AM or PM), to maintain consistent data collection and comparison of rater assessment results.

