4.2 JUSTIFICATION FOR DOSE

The therapeutic play regimen for the current study (typically 25 minutes per day; 5 days per week; 4 weeks) was established based on previous work with AKL-T01 digital treatment. Specifically, a recent pivotal trial of AKL-T01 demonstrated that this regimen resulted in significant improvements in TOVA API scores in a sample of children with attention and inhibitory control deficits (STARS-ADHD).

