6 STUDY INTERVENTION

6.1 STUDY INTERVENTION

6.1.1 STUDY INTERVENTION DESCRIPTION

AKL-T01 digital treatment is a state-of-the-art mobile video game-like platform, which deploys modern videogame graphics, engaging reward loops, and real-time adaptive mechanics to dynamically personalize difficulty based on the user's ability. AKL-T01 multitasking treatment employs perceptual discrimination attention/memory task as well as a continuous motor "driving" task. Performance on these tasks are assessed in isolation and when performed together to calculate a performance index for each individual user. A personalized multitask treatment regimen is automatically configured and delivered to the user and is optimized adaptively to increase multitask performance. As players proceed through the treatment periodic recalibration occurs to maintain an optimal difficulty level.

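### The exploratory attention endpoints in Section 3 score speed and its variability but not accuracy, so a shift towards faster, less careful responding could be read as better attention

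*Combined protocol and SAP*

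**What the plan says.** Section 3 (Objectives and Endpoints) gives one exploratory objective, improvement in attention after 4 weeks of treatment, with three endpoints:

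- "Reaction time and reaction time variability as measured by TOVA"
- "Reaction time and reaction time variability as measured by perceptual discrimination task"
- "Reaction time and reaction time variability as measured by ALK-M01 Assessment" (a misprint for AKL-M01)

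Section 6.1.1 describes the treatment: "AKL-T01 multitasking treatment employs perceptual discrimination attention/memory task as well as a continuous motor" driving task. For AKL-M01, the entry in the Section 1.3 schedule begins "AKL-M01 (AKL-T01 Monitor", and the Section 8.1 table calls it the EVO Monitor.

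The TOVA API is named as the pivotal trial's primary endpoint in Section 2.1. Section 4.2 uses it to justify the regimen: "this regimen resulted in significant improvements in TOVA API scores". It is not an endpoint in this study, although TOVA is given at Day 0 and Day 28.

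Section 4.1 states the design: "This study is a single arm, open-label, pilot study". Section 9.3 applies ANOVAs and ANCOVAs to behavioural and neural measures and names no accuracy or error score.

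The synopsis (Section 1.1) differs from Section 3. Its exploratory endpoints are the Project EVO Assessment, TOVA and the Vanderbilt, with no metric for any of them. The Vanderbilt serves a separate parent-report symptom objective that Section 3 does not carry.

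**The concern.** RT and RT variability describe how fast and how evenly a child responds, not whether the responses are correct. A child who lowers the threshold for responding can be faster and more uniform and make more errors. With no accuracy score among the endpoints, that change looks the same as better attention. The distinction matters here because the synopsis describes AKL-T01 as a treatment for inhibitory control as well as attention, and quicker responding with more errors could mean poorer control.

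Practice is a second route to the same misreading. At least one of the three instruments resembles a task that the treatment trains. Section 9.2 also limits the analysis to children who complete at least half of the prescribed treatment, so exposure to AKL-T01 is a condition of being analysed. With no concurrent control, a gain from practice cannot be told from a gain in attention.

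Leaving out the API has a smaller cost: the TOVA result cannot be set beside the pivotal trial on the scale the protocol itself cites. If the API were reported later, it would be a choice made after the data were seen.

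**Working it through.** The plan states no alpha, power, effect size or SD for these endpoints, so it has no figure to reproduce. The check is a count, a comparison of sections, and two illustrations on stated assumptions.

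**Count (Section 3).** 3 instruments × 2 measures = 6. Measures of accuracy, omission or commission errors, or API: 0. Neither the synopsis nor Section 9.3 names one.

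**Overlap with the treatment.**

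| Instrument | What the documents show |
|---|---|
| TOVA | Not described as part of AKL-T01 |
| PDT | Section 6.1.1 places a perceptual discrimination task inside AKL-T01. It does not say that this is the task used for the EEG, which Section 1.3 labels Neuroracer |
| AKL-M01 | Content not described. Overlap inferred from its names in Sections 1.3 and 8.1. Section 8.1 gives its purpose as assessing MFT activity, which does not match its use as an RT endpoint |

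**Illustration 1: can RT and RT variability both improve while accuracy falls?** I used the closed-form diffusion model for a two-choice decision, with drift v (ability), boundary a (caution) and non-decision time 0.3 s. All parameter values are assumed.

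- Accuracy = 1 / (1 + exp(−va))
- Mean RT = 0.3 + (a / 2v) · tanh(va / 2)
- RT variance = (a / 2v³) · (2y·exp(y) − exp(2y) + 1) / (exp(y) + 1)², with y = −va

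Worked case, v = 1.0:

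- a = 1.6: accuracy = 1 / (1 + exp(−1.6)) = 0.832; mean RT = 0.3 + 0.8 · tanh(0.8) = 0.831 s.
- a = 1.0: accuracy = 1 / (1 + exp(−1)) = 0.731; mean RT = 0.3 + 0.5 · tanh(0.5) = 0.531 s.

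| v | a | Accuracy | Mean RT (s) | RT SD (s) | SD / mean |
|---|---|---|---|---|---|
| 1.0 | 1.6 | 83.2% | 0.831 | 0.416 | 0.501 |
| 1.0 | 1.0 | 73.1% | 0.531 | 0.186 | 0.349 |
| 1.5 | 1.6 | 91.7% | 0.745 | 0.333 | 0.447 |
| 1.5 | 1.0 | 81.8% | 0.512 | 0.167 | 0.326 |
| 2.0 | 1.6 | 96.1% | 0.669 | 0.261 | 0.390 |
| 2.0 | 1.0 | 88.1% | 0.490 | 0.146 | 0.298 |

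At each assumed ability, lower caution makes responses faster and less variable, in absolute terms and relative to the mean, and less accurate. The documents do not describe the response format of the three tests, so this shows direction only and does not predict the trial's values.

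**Illustration 2: how often would practice alone give a significant pre-post change?** A paired t-test stands in for the within-group contrast of Section 9.3, two-sided 0.05 (assumed). The probability of significance in the direction of improvement is 1 − F(t₀.₉₇₅,ₙ₋₁), where F is the noncentral t distribution with n − 1 degrees of freedom and noncentrality dz·√n. Here dz is the mean practice change divided by the SD of change, and is assumed. Planned enrolment is 30; 24 and 20 are assumed numbers left for analysis.

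| dz (practice only) | n = 30 | n = 24 | n = 20 |
|---|---|---|---|
| 0.2 | 18% | 15% | 13% |
| 0.3 | 36% | 29% | 25% |
| 0.5 | 75% | 65% | 56% |
| 0.6 | 89% | 80% | 72% |

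A moderate practice effect with no change in attention would often reach significance.

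**The case against.** The strongest reply is that this is an exploratory objective in a pilot study. The primary and secondary endpoints are EEG power, and no success rule is attached to the RT measures. That stands and limits the weight of the point. It does not remove it, because the objective is still worded as demonstrating improvement.

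A reader might infer that any child who guesses quickly would score as improved. The documents do not support that. Every instrument is also scored on RT variability, which erratic guessing could raise, and the plan defines no direction or rule for improvement. The protection is partial: it does not cover a uniform drop in caution, the case in Illustration 1.

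A reader might also infer that four of the six measures are trained-task measures, backed by 25 × 5 × 4 = 500 minutes of practice. That goes too far. The AKL-M01 overlap rests on its name, and the PDT is not stated to be identical to the trained task. The 500 minutes are total prescribed play, shared with the driving task.

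Finally, the API does not cure the missing control. The documents expand the abbreviation but never define the score, so they do not show whether it captures accuracy. TOVA is open to retest effects too: Section 2.1 reports that all children in the feasibility study improved on it, but all had been asked to use AKL-T01, so that result does not separate practice from benefit either. This stands, and is why error scores are needed beside the API.

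**Conclusion.** The point holds for Section 3. Its attention endpoints contain no accuracy or error measure and no TOVA API, so a shift from accuracy to speed would go undetected and could be reported as improved attention. Practice on the PDT, and probably on AKL-M01, adds to the risk, because nothing in a single-arm design separates it from benefit.

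The gap is complete in number, with none of six measures covering accuracy, but modest in consequence, since it touches only an exploratory claim. How large a misreading could be is not known from the documents. The illustrated falls in accuracy, about 8 to 10 percentage points, and the practice probabilities, 13% to 89%, rest wholly on assumed parameters.

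Two stronger conclusions are not supported. One is that the whole protocol confines attention to RT: the synopsis lists TOVA and the EVO assessment without a metric, so the two lists disagree and the metrics are specified only in Section 3. The other is that API must be the lead measure, or that PDT and AKL-M01 must be barred from supporting an attention claim. These are debatable preferences for exploratory measures, and adding accuracy and labelling the results is enough.

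**What to change.** In Section 3:

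1. Add change from Day 0 to Day 28 in TOVA API, and in accuracy or error scores for TOVA, PDT and AKL-M01, reported beside RT and RT variability.
2. State that an RT gain accompanied by lower accuracy will not be interpreted as improved attention, and define before the data are examined how lower accuracy will be judged.
3. Note that PDT and AKL-M01 results may reflect practice on trained or related tasks, that TOVA is the instrument not drawn from the treatment, and that without a control none of the three separates practice from benefit.
4. Reconcile the endpoint list with the synopsis, including the metric for each instrument, the place of the Vanderbilt, and the stated purpose of AKL-M01 in Section 8.1.

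Cost: wording, plus scoring and reporting a few more exploratory measures from tests already scheduled at both visits. No visit or test is added. The attention claim becomes more cautious. The primary and secondary EEG endpoints are unaffected.

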4 STUDY DESIGN

4.1 OVERALL DESIGN

This study is a single arm, open-label, pilot study to assess midline frontal theta (MFT) power as measured by stimulus-locked electroencephalogram (EEG) before and after treatment with AKL-T01 for improving attention in pediatric participants ages 8-12 years old with attention deficit hyperactivity disorder (ADHD).

All participants enrolled in this study will not be taking ADHD medications, including stimulants, for the duration of the study. Participants who are taking ADHD medications prior to Day 0 must have been stable off of medications for at least 30 days per parent report, or washout of medications at a Screening visit 3 – 7 days prior to Day 0.

At Baseline / Day 0, all eligible participants will complete both resting-state and PDT-locked EEG, as well as the TOVA, Vanderbilt, and AKL-M01 assessments.

All participants will then play AKL-T01 for approximately 25 minutes per day, 5 days per week, for 4 weeks at home.

At Follow-up / Day 28, participants will repeat both resting-state and PDT-locked EEG, as well as the TOVA, Vanderbilt, and AKL-M01 assessments.

All study visits for each participant should be completed during the same time of day (either AM or PM), to maintain consistent data collection and comparison of rater assessment results.

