5 STUDY POPULATION

5.1 INCLUSION CRITERIA

In order to be eligible to participate in this study, an individual must meet all of the following criteria:

1. Age 8 to 12 at the time of parental informed consent
2. Male or female
3. Confirmed ADHD diagnosis at screening/baseline visit based on DSM-V criteria and established via the MINI-KID administered by a trained clinician either in person or via teleconference
4. WISC V FSIQ ≥ 70
5. Vanderbilt ADHD Diagnostic Parent Rating Scale: Must score a 2 or 3 on at least 6 items 1-9 AND must score a 4 on at least 2, or 5 on at least 1, of items 48-54 (performance questions).
6. Consistently off stimulant medication for ≥ 1 week. OR currently on stimulant medication and agree to stop taking the medication for a 1 week prior to the baseline visit and off through duration of training and post-training assessment (note: participants will only be allowed to washout of stimulant medication if in the opinion of the investigator they are currently inadequately managed on their medication and it is appropriate to stop taking their medication for the duration of the trial)
7. Consistently off Psychotropic drug for ≥ 1 month
8. Consistently off non-stimulant medication for ADHD (e.g. atomoxetine, clonidine, guanfacine) for ≥ 1 month

9. Able to follow written and verbal instructions (English) as assessed by the PI and/or study coordinator
10. Functioning at an age-appropriate level intellectually
11. Able to comply with all testing and requirements

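### For children washing out stimulants, the Schedule marks consent and assent only at Day 0, after the stop at Screening; section 4.1 and criterion 6 also disagree on the time off stimulants

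*Combined protocol and SAP*

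**What the plan says.** **Washout visit.** Section 4.1 gives children on ADHD medication two routes. Either they "must have been stable off of medications for at least 30 days per parent report", or they undergo "washout of medications at a Screening visit 3 – 7 days prior to Day 0". The Screening column of the Schedule (section 1.3) is headed "Day -7 to -3 (Participants washing out stimulants only". Its footnote reads "Screening and Baseline visits may be a combined visit for participants not washing out stimulant medication", so a washout child has a separate visit before Day 0.

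**Consent.** The Schedule row "Parent Informed consent" and the child assent row carry a mark under Enrollment / Baseline (Day 0) only. The row "Medical history" and the demographics row carry theirs under Screening.

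**Eligibility.** Criterion 6 in section 5.1 also has two routes: "Consistently off stimulant medication for ≥ 1 week", or on stimulants and willing to "agree to stop taking the medication for a 1 week prior to the baseline visit". The second route is limited to children whom the investigator considers not adequately managed on their medication and suitable to stop for the trial. Section 5.1 requires every criterion to be met. Criterion 8 separately requires at least a month off non-stimulant ADHD medication.

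**The concern.** A child aged 8 to 12 who stops a prescribed stimulant in order to join a study is undergoing a study procedure. Parental consent and the child's assent should come first, and so should collection of study history. A coordinator working down the Schedule would do these in the wrong order.

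The interval conflict matters for a different reason. Staff who follow 4.1 can produce a child who fails a mandatory inclusion criterion. A child already off stimulants can be accepted or refused depending on which section is read.

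**Working it through.** The plan states no figure to reproduce. The check compares columns and day counts.

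**1. Order of events for a washout child**

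| Event | Source | Day |
|---|---|---|
| Separate Screening visit | Schedule header and footnote | -7 to -3 |
| Stimulant stopped | 4.1 | -7 to -3 |
| Demographics, medical history | Schedule | -7 to -3 |
| Parent consent, child assent | Schedule | 0 |

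The gap from the stop to the first marked consent is 0 - (-3) = 3 days to 0 - (-7) = 7 days. The column positions can be read reliably, because rows marked under Screening and rows marked under Day 0 are distinct in the same table. No other text in the file places consent earlier: criterion 1 refers to parental consent without naming a visit, and the Statement of Compliance gives no visit timing.

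**2. Washout route: 4.1 against criterion 6**

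Assumption: the stop happens on the Screening visit day. Days off at Day 0 = 0 - (visit day). Shortfall = 7 - days off.

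| Screening day | Days off at Day 0 | Shortfall against 7 | Meets both texts? |
|---|---|---|---|
| -7 | 7 | 0 | Yes |
| -6 | 6 | 1 | No |
| -5 | 5 | 2 | No |
| -4 | 4 | 3 | No |
| -3 | 3 | 4 | No |

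One of five permitted days satisfies both. A stop later than the visit makes the shortfall larger. A stop before the visit makes it smaller, but moves the stop further ahead of marked consent.

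**3. Already-off route: 4.1 against criterion 6**

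Criterion 6 is met at 7 or more days off stimulants. Section 4.1 is met at 30 or more days, or by a stop at a Screening visit, which can give at most 7 days off.

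- 8 to 29 days off: meets criterion 6, meets neither route in 4.1. Count: 29 - 8 + 1 = 22 day values.
- Exactly 7 days off: meets both if the stop was at a Day -7 Screening visit. It fails 4.1 only if the stop was not at a Screening visit.
- 30 or more days off: meets both.

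For non-stimulants, the 30-day rule in 4.1 is in line with the one month in criterion 8, so this conflict concerns stimulants only.

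**The case against.** The strongest reply on consent is that the point rests on table cells. The Statement of Compliance binds the trial to ICH GCP and 21 CFR Part 50, the consent pages are not in the reviewed file, and a misplaced mark is plausible. The Schedule is loose elsewhere too: demographics and medical history sit only in a column headed for washout children. This limits the claim. A reader might infer that the trial plans to withdraw medication without consent, or did so. The documents do not support that. They show a Schedule that puts the steps in the wrong order. A general compliance statement does not correct it, and if the consent form gives other timing, the two would disagree.

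Second, criterion 6 requires agreement to stop and an investigator's judgement that the child is not adequately managed and can suitably stop. That clinical check lowers the likely harm, and it implies some discussion before the stop. It is not documented consent or assent.

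Third, 4.1 and the Schedule agree on 3 to 7 days, so criterion 6 could be the text to change, sparing children up to 4 days off medication. That is a fair alternative. The documents give no reason to prefer the shorter interval, and criterion 6 is the mandatory text, so it is the natural default.

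Two further readings are tempting and do not hold as faults:

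- **Adverse event recording misses the washout.** Section 8.3.1 defines the recorded events as device-related, no device is used before Day 0, and section 8.3.5 already requires inquiry at each visit and recording of deterioration from the screened condition.
- **All eligibility instruments must precede the stop.** Rating the Vanderbilt off medication is defensible, and criterion 3 already allows the diagnostic interview at Screening or baseline. Earlier checking is a suggestion only.

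**Conclusion.** The point holds in three parts.

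1. For washout children, the study-driven stop and the marked collection of history precede marked consent and assent by 3 to 7 days. This must be corrected before sites work from the Schedule. It is a statement about section 4.1 and the Schedule as printed.
2. If the stop is on the Screening visit day, one of the five permitted days meets criterion 6 and four fall 1 to 4 days short. A reader might take this to mean that four in five washout children would be ineligible. It does not: these are calendar days, and the documents give neither the share of children washing out nor how visits spread over the window.
3. A child 8 to 29 days off stimulants (22 day values, plus day 7 if the stop was not at a Screening visit) meets criterion 6 and fails 4.1.

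Parts 2 and 3 should be settled in the same amendment. No effect on the primary EEG endpoint is claimed.

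**What to change.** **Consent.** For washout participants, mark parent consent and child assent in the Screening column, with a note that both come before any study-driven stop or data collection.

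**One interval.** Use the same stimulant-free interval in 4.1, the Schedule header and criterion 6. The default is criterion 6. Suggested text for 4.1: *Participants must have been off stimulants for at least 7 days, and off non-stimulant ADHD medication for at least 1 month, before Day 0. Those stopping stimulants for the study attend Screening on or before Day -7 and stop after consent and assent, at least 7 days before Day 0.* Change the Schedule header to match, with an outer limit set by the sponsor's clinicians. If they prefer a shorter washout, amend criterion 6 instead so that the texts agree. Either way, the 30-day rule for stimulants in 4.1 and the one-week rule must become one figure.

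**Suggestion only.** Where feasible, do the MINI-KID, including Module C, at Screening after consent and before the stop. Criterion 3 already permits it. Section 8.1 gives 20 minutes, which would move from Day 0 to Screening. Checks left at Day 0 keep some risk that a child is washed out and then found ineligible.

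**Cost.** Two Schedule marks, one header and a few sentences, with no new visit. Under the default, a child is off stimulants up to 7 - 3 = 4 days longer than with a Day -3 stop, which criterion 6 already requires.
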